#### 3.6 Statistical Analysis Outline

Statistical analysis will follow the principles and consensus criteria set out in [1], including the minimum set of items that should be addressed and excluding items not relevant to this trial design (e.g. procedures for performing randomisation). The statistical tests that will be used are described in detail in Section 4.

## 4 STATISTICAL PRINCIPLES

### 4.1 Statistical Significance and Multiple Testing

*If the analysis is under a conventional (statistical hypothesis testing approach), state the level of statistical significance and the confidence intervals to be reported. Acknowledgement of the issue of multiple testing (if applicable), together with the rationale of the intention to formally or informally adjust for multiplicity. If no adjustment planned this will be stated. State which outcomes will be adjusted for multiplicity (if applicable).*

Initial analysis will assess variables for normal distribution using the Shapiro-Wilk test. All tests will be 2-tailed and  $p \leq 0.05$  will be accepted as statistically significant.

#### 4.1.1 Primary endpoint analysis

PRE/POST FFPE tissue biopsy sections stained for phospho-IGF-1R and phospho-S6 will be scanned and analysed on the HALO platform. This is a deep-learning convolutional neural network that generates H-Scores, representing the sum of the % tissues staining 0 (negative), 1+, 2+ and 3+ to generate a score range of 0-300. If the staining intensity is not sufficient to define a scoring range for H-Scores, percentage of positively stained cells will be used as output instead. To assess the significance of differences before and after xentuzumab, the PRE/POST HALO scores will be analysed using a paired t-test, or, if the paired differences do not follow a normal distribution, the Wilcoxon matched pairs signed rank test. Phospho-IGF-1R staining patterns will also be assessed by [name], to semi-quantitatively score signal in the plasma membrane, cytoplasm and nucleus. Existing data from our group suggest that nuclear IGF-1R associates with higher stage prostate cancer [3] .

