**Table 1: Estimand-to-analysis table template**

**Primary Objective:** Assess the amount of IGF pathway inhibition induced by xentuzumab

**Estimand:** The amount of IGF-1 blockade induced by xentuzumab measured through automated immunohistochemistry (IHC) analysis of IGF-1 receptor activation (phospho-IGF-1R) and downstream activation marker phospho-S6.

**Treatment:** Xentuzumab infusion (1000mg), once weekly for a minimum of 4 weeks

Estimand	Analysis
Target population	Analysis set
Men ≥ 18 years old with prostate cancer who are scheduled for radical prostatectomy.	All participants who meet trial eligibility criteria and initiate treatment.
Variable	Outcome measure
H-Score or % of positively stained cells for phospho-IGF-1R and phospho-S6 as measured by IHC.	Statistical significance of the difference between IGF1 axis activity in PRE treatment and POST treatment samples.  All participants who have sufficient material in the diagnostic (PRE-treatment) and in theatre (POST-treatment) biopsy cores for IHC analysis will be included, provided intercurrent events have not affected their ability to meet trial eligibility criteria.
Handling of intercurrent events	Handling of missing data
Intercurrent events which prevent the patient from having in theatre (POST-treatment) biopsy cores available for IHC analysis after at least 4 doses of xentuzumab will preclude the patient from analysis of the primary endpoint. This does not fall under the	Missing data will not be imputed. Patients whose samples are not sufficient to provide a score at baseline and after treatment will be excluded from the primary endpoint analysis. For other endpoints/analyses, Chief Investigator  Sensitivity analysis: NA, data will not be imputed.

typical handling of intercurrent events due to the single arm design of this trial.

Intercurrent events that do not prevent the patient from having in theatre (POST-treatment) biopsy cores available for IHC analysis, and would not affect the patient's trial eligibility, will be assessed by the Chief Investigator.

Population-level summary measure	Analysis approach

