Sample size calculations were repeated in October 2022 based on newly acquired preclinical data quantifying the amount of IGF axis pathway inhibition achieved by xentuzumab. This equates to the WINGMEN trial primary endpoint: the amount of IGF axis pathway inhibition. In a preclinical prostate cancer model, xentuzumab suppressed IGF-1R phosphorylation (pIGF-1R) with an effect size of 0.68 (G\*Power v3.1). Using Wilcoxon signed rank test (matched pairs, 2-tailed), recruitment of 20 patients (20 matched pre/post-treatment pairs) will be significant at the 5% level with 80% power. Using a one-tailed test, based on the hypothesis that xentuzumab will reduce pIGF-1R, we will need 16 patients (16 matched pairs of tissue). Therefore, we aimed to recruit 20-30 patients in case some prostate biopsies are inadequate or unsuitable for translational studies.

	n	Median serum IGF-1 nmol/l		n	Median serum IGF-1 nmol/l	p value
Benign epithelium						
IGF-1R score ≤ 10	77	16.54	IGF-1R score > 10	60	16.68	p=0.871
Malignant epithelium						
IGF-1R score ≤ 14	79	15.58	IGF-1R score > 14	60	17.07	p=0.038

**Table 2. Serum IGF-1 associates with IGF-1R immunoreactive score in malignant prostate epithelium.** Immunoreactive scores (calculated as described in [3] were divided by the median values. IGF-1R scores were generally higher in malignant epithelium, consistent with our earlier report of IGF-1R overexpression in prostate cancer [4], hence cut point of 14 in malignant epithelium vs 10 in benign epithelium. NB Two samples had no benign epithelium in the scored sections ([name], [name], [name], unpublished).

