#### 3.4.1 Primary endpoint

The primary endpoint, the amount of IGF axis pathway inhibition, will be assessed by batch analysis using automated IHC for phospho-IGF-1R and downstream marker phospho-S6. Multiple rounds of validation have confirmed that the selected antibodies are stable, providing reproducible signal in multiple prostate samples and analytical runs. Analysis of freshly cut paired sections of diagnostic biopsy and in-theatre prostate biopsy cores from a non-trial subject confirmed that the selected phospho-epitopes are stable between these two time-points. The paired diagnostic (PRE-treatment) and in theatre (POST-treatment) biopsy cores of the two trial patients identified above will be analysed in the same staining run, alongside a negative IHC control. If the results are satisfactory, sections will be cut from the remaining PRE/POST biopsy core pairs and freshly stained for phospho-IGF-1R and phospho-S6. Again, each pair of tissues will be analysed in the same staining run, alongside a negative control.

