#### 3.5 Blinded analysis

There will be no blinding for treatment: all trial subjects will be treated with xentuzumab. Research staff of the Translational Histopathology Lab will be blinded. [name] lab members will not be blinded as to whether the samples are PRE or POST xentuzumab.

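### The fallback of the primary score from H-Score to percent positive has no stated threshold, decision-maker or time point, and nothing supplied keeps the choice masked to PRE/POST

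*SAP*

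**What the plan says.** The estimand table (SAP section 2, Table 1) defines the primary variable on either of two scales: "H-Score or % of positively stained cells for phospho-IGF-1R and phospho-S6 as measured by IHC". SAP 4.1.1 ranks them. The H-Score, range 0 to 300, is the default, and the fallback reads: "If the staining intensity is not sufficient to define a scoring range for H-Scores, percentage of positively stained cells will be used as output".

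On masking, SAP 3.5 says that Translational Histopathology Lab staff will be blinded. It then says that for another group, whose name is removed, "lab members will not be blinded as to whether the samples are PRE or POST xentuzumab". SAP section 6 gives the HALO quantification of the scanned images to a doctoral student of a laboratory whose name is also removed, with later review alongside the trial pathologist. The pathologist's blinding is not stated. The same section adds that one or both markers may be used to quantify inhibition, depending on that assessment.

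On timing, SAP 3.4 and 3.4.1 have two trial patients' pairs stained first as a check of the tissue pipeline, and then: "If the results are satisfactory, sections will be cut from the remaining PRE/POST biopsy core pairs". No criterion for satisfactory is given.

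SAP 6.3 (sensitivity analysis) deals with controls and spare material. SAP 6.5 plans no supplementary analysis of the primary endpoint. So nothing in the supplied text requires the scale not chosen to be reported.

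**The concern.** Staining intensity can be judged only on stained sections. Unless the rule is fixed on other tissue, the scale is settled when trial images already exist. If the person judging intensity also knows which image is PRE and which is POST, the judgement could be influenced, even without intent, by how the two compare.

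Two things are at stake. One is the error rate of the primary test: a choice between two correlated scales that is informed by the difference gives more than one chance at significance. The other is the estimate itself. The objective is the amount of inhibition, and a change on a 0 to 300 scale is not the same quantity as a change on a 0 to 100 scale. In an open-label study without a control arm, masked scoring under a fixed rule is the main protection that the primary comparison can have.

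**Working it through.** **1. The plan's own figure.** SAP 3.2 reports that "xentuzumab suppressed IGF-1R phosphorylation (pIGF-1R) with an effect size of 0.68" and that "recruitment of 20 patients (20 matched pre/post-treatment pairs) will be significant at the 5% level with 80% power", by Wilcoxon signed rank test. I used paired noncentral-t power with the effective number of pairs n × 3/π (the Wilcoxon test's efficiency for normal differences).
- Two-sided, n = 20: 20 × 3/π = 19.10; noncentrality 0.68 × √19.10 = 2.97; 18.10 degrees of freedom; critical value 2.100; power 80.3%. With n = 19, power is 78.0%. So 20 reproduces.
- One-sided, n = 16: 16 × 3/π = 15.28; noncentrality 0.68 × √15.28 = 2.66; critical value 1.759; power 81.2%. With n = 15, power is 78.7%. So the one-tailed statement, "we will need 16 patients (16 matched pairs of tissue", also reproduces.

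The sample size is not in question here. It stands if an effect size of 0.68 applies on whichever scale is used.

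**2. Inputs for the error rate.**
- Level and sidedness: 5%, and "All tests will be 2-tailed" (SAP 4.1).
- Pairs: n = 20 (SAP 3.2).
- Correlation ρ between a patient's PRE/POST change on the H-Score and on percent positive: **not in the documents; assumed, range 0.5 to 0.99**.

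**3. Worst case, one marker.** Under no drug effect, draw standard normal changes x on one scale and y = ρx + √(1 − ρ²)·e on the other, for 20 patients. Compute t = mean/(SD/√20) on each. Count a false positive if either |t| exceeds 2.093 (the 97.5% point of t with 19 degrees of freedom). One million simulated trials per row; Monte Carlo standard error about 0.03 percentage points:

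| Assumed ρ | Type I error if the better scale is always taken |
|---|---|
| 0.5 | 9.2% |
| 0.7 | 8.5% |
| 0.8 | 7.9% |
| 0.9 | 7.1% |
| 0.95 | 6.5% |
| 0.99 | 5.7% |

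The bound for two independent scales is 1 − 0.95² = 9.75%. With 30 pairs the results are much the same (8.4% at 0.7, 7.1% at 0.9; 200,000 trials).

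**4. What correlation is plausible.** In a simple model, both scores were derived from one latent staining intensity with assumed cut-points and spreads (40,000 trials, n = 20). It gave correlations of 0.83 to 0.97 and a worst-case error of about 6.0% to 7.5%.

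**5. A switch unrelated to the difference.** With the scale switched at random in half of the trials, independently of the PRE/POST changes, the error was 4.98% at ρ = 0.7 and 5.03% at ρ = 0.9 (200,000 trials). What matters is whether the choice is shielded from the PRE/POST difference, not that a fallback exists.

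**The case against.** The strongest reply is that this is a one-way technical fallback, written in advance. The H-Score is the default, and the trigger is inadequate intensity, not the PRE/POST difference or the p-value. That stands, and it rules out several stronger readings.

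- *Unblinded staff choose the scale.* A reader might infer this from SAP 3.5 and section 6 together. Neither says who decides. With names removed, that the scoring laboratory is the unblinded one is likely but cannot be shown, and running HALO is not the same act as choosing the scale.
- *Weak POST staining, the hoped-for drug effect, itself triggers the switch.* The text does not say so. Weak cells can be scored 0 or 1+, a low H-Score is valid, and PRE tissue stained in the same run would still supply a range. The natural reading is a general lack of intensity, although the SAP does not settle it.
- *The two pilot pairs are used to pick the scale.* SAP 3.4 describes a pipeline check, and nothing links it to that choice.
- *The error rate is 7% to 8.5%.* Those figures model always taking the better scale, which the SAP does not plan. Where intensity cannot separate 1+, 2+ and 3+, nearly all positive cells fall in one class and the H-Score is close to a multiple of percent positive. Correlation is then near 1 and inflation is least exactly where the fallback is legitimate.

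Other safeguards help less. Automated scoring, pathologist review and the independent repeat analysis (SAP section 7) check the execution, but none is said to set or mask the scale. SAP section 1 says that full outcome definitions are in Data Definitions and Tables. That document was not supplied and may contain the threshold, but the fallback sentence in SAP 4.1.1 does not point to it.

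**Conclusion.** The point holds as a gap in protection, not as evidence of a result-driven choice. The supplied text leaves the threshold, decision-maker, time point and unit of the scale switch open. It does not show that the choice or the quantification is masked to PRE/POST.

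The possible cost to the primary test is moderate. The worst case per marker at 20 pairs is about 8.5%, 7.1% or 5.7% instead of 5%, at assumed correlations of 0.7, 0.9 or 0.99, and there is no inflation if the choice is independent of the PRE/POST difference. These figures assume normal changes, paired t-tests on both scales and always taking the better scale. They do not count the second marker. The sample size is unaffected. If Data Definitions and Tables already holds a numeric rule applied to masked images, what remains is a missing cross-reference.

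The change is still worth making: it is cheap, and the study has no control arm to expose a scoring bias.

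**What to change.** In SAP 4.1.1 and Table 1:

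1. For each marker, choose one scale by a stated intensity rule. Set the rule on the validation tissue and controls (SAP 5.6.1), or on code-masked trial images if the trial slides must be seen to judge intensity. The second route avoids committing the trial to a score that its own slides cannot support.
2. Name who applies the rule, and date the decision before any unmasked PRE/POST comparison.
3. Apply the chosen scale to all pairs for that marker, with no switching by sample.
4. Run the HALO quantification and the two-patient check on images with PRE/POST labels masked. Judge the check on controls and technical quality.
5. Report the other scale as a sensitivity analysis where it can be computed. If no scoring range can be defined, the H-Score will not be available, and the report should say so.
6. If Data Definitions and Tables already contains the rule, cite it at the fallback sentence.

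The cost is coded image labels, a small amount of extra analysis and SAP wording. It needs no additional staining, tissue or patients.

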14 STATISTICAL ANALYSIS PLAN

Change in phospho-AKT (or downstream target) and phospho-IGF-1R immunoreactive score before and after treatment will be assessed using the Wilcoxon matched pairs signed rank test. Changes in PSA and other IHC markers including Ki67 index, IGF-1R, RRM2, CD31 and immune markers CD4, CD8, PD-L1, FoxP3 will be assessed using a paired samples t-test or a Wilcoxon matched pairs signed rank test if normality assumptions are not satisfied.

The severity of adverse events (AE) will be graded using the National Cancer Institute Common Terminology Criteria for Adverse Events (NCI CTCAE) version 5.0. Adverse events will be summarised; highest grade per patient AE summaries will be presented, according to whether the AEs are considered treatment-related or not, and over time.

A detailed statistical analysis plan will be written and will be finalised before any analysis is undertaken. The analysis plan will be written in accordance with current Standard Operating Procedures.

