Statistical significance of the difference between IGF1 axis activity in PRE and POST treatment samples.	
PRE/POST HALO scores will be analysed using a paired t-test, or, if the paired differences do not follow a normal distribution, the Wilcoxon matched pairs signed rank test.
 
Sensitivity analyses: Data will be tested for normal distribution and the appropriate test chosen accordingly (i.e. there is no assumption of normality). The appropriate sample size for 80% power was calculated as in Section 1.4.

Strategies defined in E9 (R1) include treatment policy, while on treatment, principal stratum and hypothetical

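### The SAP lets a normality check choose the primary test, although the protocol fixes the Wilcoxon signed rank test and the trial is powered on it

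*SAP*

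**What the plan says.** Protocol section 14 treats two groups of markers differently in consecutive sentences. For the primary markers, the change in "immunoreactive score before and after treatment will be assessed using the Wilcoxon matched pairs signed rank test", with no normality step. Changes in PSA and the other tissue markers "will be assessed using a paired samples t-test or a Wilcoxon matched pairs signed rank test if normality assumptions are not satisfied".

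SAP 4.1.1 applies the second kind of rule to the primary endpoint: the scores are "analysed using a paired t-test, or, if the paired differences do not follow a normal distribution, the Wilcoxon matched pairs signed rank test". Table 1 repeats this as the analysis approach. Under its sensitivity-analysis label it adds that normality will be tested and the test picked to suit. The check is named in SAP 4.1: "Initial analysis will assess variables for normal distribution using the Shapiro-Wilk test".

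The power statement did not move with the test. SAP 3.2 still reads "Using Wilcoxon signed rank test (matched pairs, 2-tailed), recruitment of 20 patients", matching Protocol 13.1 (effect size 0.68, 80% power, alpha 0.05). The population-level summary measure in Table 1 is "Statistical significance of the difference between IGF1 axis activity in PRE and POST treatment samples".

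The version table in SAP 1.2 ties the SAP to Protocol 2.0 and records no changes, because this is the first issue.

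**The concern.** A primary analysis should be identifiable before the data are seen. Here the protocol names one test and the SAP names two, with the trial data deciding between them. The SAP also disagrees with itself, because it is powered on Wilcoxon but defaults to the t-test. Phospho-IGF-1R and phospho-S6 go through the check separately, so one may be reported with a t-test and the other with Wilcoxon.

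The two tests answer the same question only when the paired differences are symmetric. The t-test concerns the mean change and Wilcoxon the pseudo-median change. The objective is the amount of pathway inhibition, yet Table 1 names neither. A reader of the report would therefore have a p-value from a test chosen by the data, and no pre-specified size of effect to go with it.

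**Working it through.** **Inputs.** Effect size 0.68, 20 pairs, two-sided alpha 0.05 and 80% power (Protocol 13.1, SAP 3.2). The Shapiro-Wilk threshold is taken as 0.05. SAP 4.1 states no threshold for the check itself, but sets p ≤ 0.05 for all tests. The documents give no distribution for the paired differences, so the shapes below are assumptions.

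**1. The plan's own figure.** Use the noncentral t distribution with n multiplied by the asymptotic relative efficiency of Wilcoxon under normality, 3/π.
- Effective n = 20 × 3/π = 19.10
- Noncentrality = 0.68 × √19.10 = 2.97
- Power = 0.803

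The stated 20 pairs reproduce. The one-tailed 16 pairs also reproduce (power 0.812). A paired t-test would need 19 pairs (0.800) and has power 0.822 with 20. The sample size therefore holds under either test.

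**2. The two-stage rule.** The simulation used 20,000 trials per scenario with n = 20 and Shapiro-Wilk at 0.05. Each trial took the t-test if the check passed, otherwise the exact signed rank test. The exact test's two-sided size at n = 20 is 4.84%.

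| Shape of differences | Sent to Wilcoxon | Type I error: t / Wilcoxon / two-stage | Power at 0.68 SD: t / Wilcoxon / two-stage | t and Wilcoxon disagree at 0.68 SD |
|---|---|---|---|---|
| Normal | 5% | 4.9 / 4.6 / 5.0% | 81.8 / 80.1 / 81.8% | 4.2% |
| Laplace | 26% | 4.4 / 4.5 / 4.6% | 81.9 / 87.2 / 85.7% | 6.8% |
| t(3) | 34% | 4.5 / 4.9 / 5.2% | 86.5 / 93.5 / 92.7% | 7.9% |
| Exponential | 84% | see step 3 | 95.3 / 89.2 / 89.3% | 7.8% |

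Simulation error is about 0.15 points at 5% (√(0.05 × 0.95 / 20,000)) and 0.28 points at 80%. Two further skewed shapes, reflected exponential and lognormal, give two-stage power of 84.1% and 98.9%, with disagreement of 9.1% and 2.6%.

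The two-stage verdict differs from a fixed Wilcoxon verdict in about 0 to 4% of trials at 0.68 SD. The gap is largest for normal differences, where the rule nearly always uses the t-test. It is near zero for exponential differences, where it nearly always uses Wilcoxon.

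**3. Skewed differences with a true mean of zero.** For the exponential shape, rejection is 8.2% (t), 13.0% (Wilcoxon) and 13.1% (two-stage). The excess for Wilcoxon arises because the pseudo-median is not zero when the mean is. This shows that the tests target different parameters under skew.

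**4. Different tests for the two markers.** If both markers had the same shape and were independent, the chance of a split is 2p(1 − p), where p is the share sent to Wilcoxon. That is 2 × 0.05 × 0.95 = 9.5% for normal and 2 × 0.34 × 0.66 = 45% for t(3). Positive correlation between the markers would lower these.

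**The case against.** The strongest reply is that the SAP rule is a written algorithm, not analyst discretion, and that it does almost no numerical harm. That stands. For normal differences the two-stage type I error is 5.0%, and power stays above the planned 80% in every shape tried. A t-test chosen in advance and justified would also be defensible.

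Several stronger readings are tempting and are not supported:

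- **Inflated type I error or a wrong sample size.** Steps 1 and 2 show neither.
- **The normality check is what leaves the effect undefined.** Table 1 names no parameter whichever test is run. SAP section 6 says mean percentage change may be used to quantify inhibition, and does not tie that to the normality check. The missing measure is a separate gap in Table 1, and fixing Wilcoxon alone would not close it.
- **SAP 4.1 contradicts 4.1.1 because one checks variables and the other paired differences.** SAP 4.1 is a general statement. Table 1 and 4.1.1 are specific to the primary endpoint, both refer to paired differences, and the specific text governs.
- **The test was changed after results were seen.** The SAP is dated June 2024, after recruitment closed, but SAP 3.4.1 describes primary staining of the trial pairs as still to come. Protocol section 14 requires only that the SAP be final before any analysis.
- **Wilcoxon would protect a statement about mean change.** Step 3 shows that it would not under skew. It has to be paired with its own estimate.

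Presentation of the primary endpoint is delegated to the separate Data Definitions and Tables document, which is not available here. Estimates and intervals may already be specified there.

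**Conclusion.** The inconsistency is in the text and does not depend on any simulation. The protocol and both power statements use Wilcoxon, while the SAP uses a normality-gated t-test and gives no reason. Table 1 also leaves the amount of inhibition without a named parameter.

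The practical size is modest. The choice between the two tests changes the verdict in about 4 to 8% of trials at 0.68 SD across the normal, Laplace, t(3) and exponential shapes. Using the two-stage rule in place of fixed Wilcoxon changes it in about 0 to 4%. These figures assume 20 evaluable pairs, a 0.05 threshold for Shapiro-Wilk and the shapes listed. The point should be corrected for pre-specification, consistency and interpretability, and should not be presented as an error-rate or sample-size problem.

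**What to change.** In SAP Table 1 and 4.1.1:

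- Name the Wilcoxon signed rank test as the only primary test for both markers.
- Remove the Shapiro-Wilk gate for the primary endpoint, and limit the general sentence in SAP 4.1 to the other endpoints.
- Replace the summary measure in Table 1 with the Hodges-Lehmann paired change and its 95% CI.
- Keep the paired t-test, with the mean change, as a labelled sensitivity analysis.

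If the sponsor prefers the t-test, the SAP should fix that single test for both markers, name the mean change with its 95% CI, and record and justify the departure from Protocol section 14.

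The cost is SAP wording. Fixing Wilcoxon gives up about 2 points of power if the differences are exactly normal (80.1% against 81.8% in simulation), still at the planned 80%. The 20 pairs do not change.
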